## 8 Demographic and other baseline characteristics

The comparability of the treatment groups will be assessed by the demographic and baseline characteristics. These include but are not restricted to

- demographics (age, sex, race, ethnicity)
- effective use of birth control
- habits (physical activity, smoking)
- assessment of blinding
- medical history and concomitant diseases
- physical examination
- vital signs

All baseline variables will be reported using descriptive statistics. If feasible, the baseline distribution will be evaluated with inferential statistics for flagging purposes. One-way ANOVA (or appropriate non-parametric test) between the treatment groups will be applied for continuous variables such as age. For categorical variables chi-square or Fisher's exact test will be used.

## 9 Prior and concomitant medication/treatment

Concomitant medication and treatments will be summarized by treatment group using ATC classification.

## 10 Extent of exposure and compliance

Extent of exposure will be evaluated descriptively as duration of study treatment (number of days).

Compliance will be assessed by summarizing the number of used and unused sachets returned as percentages of the total number of sachets dispensed. Product recovery from fecal samples will be evaluated by qPCR.

## 11 Analysis of efficacy

### 11.1 Primary efficacy variables

The primary efficacy analysis is comparing the incidence of rhinovirus-associated illness episodes (Yes/No) between the treatment groups. A rhinovirus-associated illness episode is detected in case both the following criteria are met:

- 1) Rhinovirus infection: Isolation of the challenge virus on any of the 5 days (study days 1-5) after virus challenge OR a four-fold rise in the neutralizing antibody titer to the study virus (day 28).
- 2) Symptomatic illness: Based on the modified Jackson criteria a total symptom score of at least 6 over the 5 days (sum of study days 1-5) after virus challenge AND either three days of rhinorrhea or the subjective impression that they have had a common cold illness.

The relationship between the treatment and the incidence of rhinovirus-associated illness episodes will be tested by using a chi-square test. In case the cell frequencies, such as the expected number of subjects experiencing an illness episode or the expected number of subjects without any episodes in either of the treatment groups, turn out 5 or lower, a Fisher's exact test will be used for the comparison instead, which is a more suitable method with low expected frequencies.

### 11.2 Secondary efficacy variables

#### 11.2.1 Duration of illness

Duration of illness is defined as the time between the virus challenge and the end of the illness episode in volunteers who met the modified Jackson definition of symptomatic illness (11.1). The last day of the illness will be defined as the first day of the two consecutive days with a total symptom score  $\leq 1$  that occurs after the subject has met the symptom criteria for a Jackson cold. In case the symptom score is  $\leq 1$  on the last day of symptom score assessment, the end of illness will be set to the last assessment day. If the illness continues  $>14$  days (symptom score  $>1$  on the last day of assessment), the length of illness will be set as 15 days.

The main analysis will be done using the Ill dataset. Additionally, analysis will be repeated with PP and ITT datasets. For these additional analyses using datasets including also non-ill subjects, the duration of illness will be set to zero for subjects experiencing no illness.

Illness duration will be analysed by comparing the group mean durations with a two-sample independent t-test. In case the durations are not normally distributed a non-parametric Wilcoxon-Mann-Whitney test will be used for the comparison.

#### 11.2.2 Incidence of infection

Incidence of infection (Yes/No) will be defined as the isolation of the challenge virus on any of the 5 days (study days 1-5) after virus challenge or a four-fold rise in neutralizing antibody titer to the study virus.

Incidence of infection will be analysed exactly the same way as the primary response (section 11.1).

#### 11.2.3 Viral load during infection

Viral load will be assessed by comparing the quantitative virus titer in nasal lavage between the probiotic and placebo groups. For this calculation, subjects with no virus isolate on a study day will be defined as having a quantitative titer of  $-0.5$  ( $\log_{10}$ ).

The quantitative viral titer load during infection will be evaluated with repeated measures analysis of variance model (RM-ANOVA) including the daily titer load as a response ( $\log_{10}$ ), treatment, day and the interaction of day and treatment as explanatory variables. The random effect of subject will be included in the model. Model assumptions will be checked with model diagnostics and normality plots. In case the assumptions of the RM-ANOVA model are severely violated (after common transformations), generalised linear mixed models for repeated measurements with more appropriate distribution assumptions (e.g. poisson or negative binomial) will be fitted. The main interest of this analysis is the overtime treatment effect.

#### 11.2.4 Proportion shedding the virus

Virus shedding will be defined as the isolation of the challenge virus on any of the 5 days (study days 1-5) after virus challenge.

Proportion shedding the virus will be analysed exactly the same way as the primary response (section 11.1).

#### 11.2.5 Acute illness period total symptom score

Daily total symptom score during study days 1-5 will be analysed based on the Jackson criteria with repeated measurements models similarly than the quantitative viral titer load (11.2.3). The main interest of this analysis is the overtime treatment effect. Individual symptom scores will be evaluated as exploratory endpoints (described in 11.3).

#### 11.2.6 Total symptom score based on the Jackson criteria

Daily total symptom score during study days 1-14, will be analysed based on the Jackson criteria with repeated measurements models (like in 11.2.3). The main interest of this analysis is the overtime treatment effect.

The secondary analyses are ordered in a hierarchical order by their clinical importance as described in this section. Thus, no multiplicity correction is needed, and a p-value  $\leq 0.05$  can be stated as statistically significant as long as the hierarchy is being taken into account with the conclusions.

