8 STATISTICAL METHODS

8.1 ESTIMATION OF SAMPLE SIZE

The sample size for this study was calculated on the primary endpoint of rhinovirus-induced illnesses. The challenge model results in an infection rate of approximately 90% in the control group. Approximately 67% of the infected volunteers (60% of all challenged volunteers are expected to develop a symptomatic illness and will meet the study definition of a rhinovirus-induced illness. A sample size of 95 completed subjects/arm would be expected to detect a reduction in rhinovirus-induced illness of 20% (from 60% to 40%) with 80% power with $p_{\alpha} = 0.05$.

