8.4.2 SECONDARY ANALYSIS

The secondary analyses will be concentrating on duration of illness, incidence of infection, viral load during infection and proportion shedding the virus.

The duration of illness between the treatment groups will be investigated by comparing the group mean durations with a two sample independent t-test. In case the durations are not normally distributed a non-parametric Wilcoxon-Mann-Whitney test will be used for the comparison.

The dichotomous variables, proportion of infection incidence and virus shedding (days 1-5), will be both evaluated exactly the same way as the primary response (described in 8.4.1).

The quantitative viral titer load during infection will be evaluated with repeated measures analysis of variance model (RM-ANOVA) including the daily and overall (study days 1-5) titer load as a response, treatment, day and the interaction of day and treatment as explanatory

variables. The random effect of subject will be taken into account in the model. Model assumptions will be checked with model diagnostics and normality plots.

The secondary analyses are ordered in a hierarchical order by their clinical importance as described in 6.3. Thus no multiplicity correction is needed and a p-value ≤ 0.05 can be stated as statistically significant as long taking into account the hierarchy with the conclusions.

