## 5 Statistical hypotheses

The purpose of this study is to support the evidence that the probiotic supplementation is more effective than the effect of placebo in reducing the incidence of rhinovirus-associated illness episodes, i.e., the null-hypothesis to be tested is

$H_0$  : There is no relationship between the treatment and the incidence of rhinovirus-associated illness episodes

$H_1$  : There is a relationship between the treatment and the incidence of rhinovirus-associated illness episodes

The effect of probiotic supplementation is considered shown if the two-sided p-value of the primary statistical analysis is less than 0.05.

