## 7 General statistical considerations

In the statistical analyses, a p-value less than 0.05 will be considered as statistically significant. If not stated otherwise, all tests will be performed as two-sided tests and two-sided 95% confidence intervals will be produced for the treatment differences. No adjustments for the p-values will be made. Missing values will not be imputed in the analyses.

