## 15 Deviations from the analyses planned in the study protocol

Secondary analyses of 11.2.5 and 11.2.6 for Acute and Total Symptom Score based on the modified Jackson criteria were added to the hierarchy. Also, individual symptom scores based on the Jackson criteria were added to the exploratory endpoints (11.3).

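### The secondary hierarchy has no written stopping step and no link to the primary test, so the ordering alone does not support the statement that no multiplicity correction is needed

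*SAP*

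**What the plan says.** Protocol 8.4.2 ranks four secondary analyses in the order of section 6.3: duration of illness, incidence of infection, viral load, proportion shedding. From the ranking it infers: "Thus no multiplicity correction is needed and a p-value" of 0.05 or less counts as significant, with the hierarchy to be kept in mind in the conclusions.

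SAP 11.2.6 closes the secondary section with nearly the same statement for six analyses, 11.2.1 to 11.2.6. A p-value of 0.05 or less "can be stated as statistically significant as long as the hierarchy is being taken into account with the conclusions". The two extra analyses are the symptom scores over days 1-5 and days 1-14, which according to SAP 15 "were added to the hierarchy".

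SAP 7 adds: "No adjustments for the p-values will be made". The rule for the primary hypothesis stands apart in SAP 5: "The effect of probiotic supplementation is considered shown if the two-sided p-value of the primary statistical analysis is less than 0.05". It does not mention the secondaries, and the hierarchy paragraphs do not mention the primary. SAP 20.2 gives a main dataset for each endpoint but no testing rule.

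**The concern.** In a fixed-sequence procedure it is the stop that protects the error rate: once one test fails, no later test can produce a claim. The order only says where the stop falls. Both documents give the order, omit the stop, and draw the conclusion that depends on it. The condition that remains, taking the hierarchy into account in the conclusions, is not a decision rule. Two statisticians could apply it to the same data and report different endpoints as significant.

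The relation to the primary is also left open. The hierarchy covers the secondaries only, so a non-significant primary does not block secondary claims under either document.

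This could well arise here. Protocol 1.1 reports that the earlier rhinovirus challenge trial of the same strain found a lower virus titer and less shedding (76% against 91%, p=0.04), and no effect on symptom severity. The present primary requires symptomatic illness. Viral load and shedding stand third and fourth among the secondaries, behind duration and infection. A failed primary followed by a positive shedding result is a realistic outcome, and the plan does not say whether that result may be called statistically significant.

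**Working it through.** **Inputs from the documents.** Two-sided 0.05 for the primary (SAP 5) and for every other test unless stated otherwise (SAP 7: "In the statistical analyses, a p-value less than 0.05 will be considered as statistically significant"); no p-value adjustment (SAP 7); one primary; six secondaries in the SAP, four in the protocol. Neither document states a family-wise error rate or any correlation between endpoints, so the correlations below are assumptions.

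**The plan's own figure.** Protocol 8.1 plans on 95 completed subjects per arm for a "reduction in rhinovirus-induced illness of 20% (from 60% to 40%) with 80% power". The unpooled normal approximation, two-sided 0.05, gives

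n = (1.960 + 0.842)² × (0.6×0.4 + 0.4×0.6) / (0.6 − 0.4)² = 7.849 × 0.48 / 0.04 = 94.2, rounded up to 95.

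The figure is reproduced. The pooled formula gives 97, and power at 95 per arm is 79.2%. The sample size therefore spends the whole two-sided 0.05 on the primary, and nothing below alters it.

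**Error rates with every null true, independent tests.**
- No stop, the protocol's four secondaries: 1 − 0.95⁴ = 18.5%
- No stop, the SAP's six secondaries: 1 − 0.95⁶ = 26.5%
- No stop, primary plus six: 1 − 0.95⁷ = 30.2%
- Stop within the secondaries, no gate on the primary: a first false claim can come only from the primary or from the first secondary, so 1 − 0.95² = 9.75%. Whatever the correlation, the bound is 0.05 + 0.05 = 10%.
- Stop and gate: a first false claim can come only from the primary, so 5%.

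**The same with correlated tests.** One million simulated sets of seven two-sided z-tests, all pairs equally correlated:

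| Rule | 0 | 0.3 | 0.5 | 0.7 | 0.9 |
|---|---|---|---|---|---|
| No stop, six secondaries | 26% | 24% | 21% | 16% | 11% |
| No stop, primary plus six | 30% | 27% | 23% | 18% | 11% |
| No stop: some secondary significant, primary not | 25% | 22% | 18% | 13% | 6% |
| Stop within secondaries, no gate: primary plus secondaries | 9.7% | 9.5% | 9.1% | 8.4% | 7.0% |
| Stop and gate | 5% | 5% | 5% | 5% | 5% |

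With a stop, error within the secondary family alone is 5% at any correlation.

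**Which correlations are plausible.** Several endpoints overlap by definition. The shedding criterion is one arm of the infection criterion (SAP 11.2.2, 11.2.4), viral load is measured by nasal lavage in the same period (11.2.3), and the day 1-5 scores are part of the day 1-14 scores (11.2.5, 11.2.6). For the no-stop rows, independence is therefore close to a worst case; 0.9 for every pair is also unlikely.

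**The cut-off.** SAP 5 and SAP 7 require p below 0.05. Protocol 8.4.1, protocol 8.4.2 and SAP 11.2.6 accept p equal to 0.05.

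**The case against.** The best defence is that a hierarchical order followed by an inference that no correction is needed is familiar shorthand for fixed-sequence testing. The permission is conditional: the hierarchy must be taken into account. A reader might infer that the plan lets any secondary with p of 0.05 or less be declared significant whatever came before it, so that the no-correction statement is simply false. The documents do not go that far. They leave the condition undefined, and on the fixed-sequence reading the statement holds within the secondaries.

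Four further inferences also go too far:
- That the false-claim rate is 30%. This needs the literal reading, independent tests and the planned 5% for the primary counted in.
- That lengthening the list from four to six inflates error. It does so only without a stop. The two additions were disclosed and placed last, where a fixed sequence makes them harmless.
- That the likeliest positive results sit at the bottom. The bottom two are symptom scores, and the earlier trial saw no effect on symptom severity.
- That SAP 7's refusal to adjust p-values shows the defect. A fixed sequence needs no adjustment.

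It is also fair to say that this is a phase II trial, that neither document claims family-wise control across primary and secondaries, and that under SAP 5 only the primary can show the effect. A secondary p-value cannot meet that criterion.

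What remains is that no stop is written, the fixed sequence has to be supplied by the reader, and even then a secondary may be called statistically significant beside a failed primary.

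**Conclusion.** The concern holds as an undefined procedure. The ordering is offered as the reason for making no correction, but the two rules that would make it sufficient are absent from both documents. On the fixed-sequence reading the only excess is the missing gate: about 7-10% instead of 5% across primary and secondaries. On the literal reading it is about 11-30%. Both ranges rest on assumed equal correlations from 0.9 to 0 and on every null being true.

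The gap affects which secondary results the report may call significant. It does not affect the validity of the primary test, the 95 per arm or the order of the endpoints. It should be corrected, and wording is enough.

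**What to change.** Put one rule in SAP 11.2 and protocol 8.4.2 before the treatment code is opened:

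> If the primary test in the PP dataset gives two-sided p < 0.05, the secondary endpoints are tested in the order 11.2.1 to 11.2.6, each in its main dataset (20.2), at two-sided 0.05. Testing stops at the first p ≥ 0.05. All later p-values, and all secondary p-values if the primary is not significant, are descriptive.

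In the protocol, refer to the matching endpoints. With this rule in place the sentence that no multiplicity correction is needed is correct and may stay, as may the no-adjustment sentence in SAP 7. Use one cut-off throughout both documents.

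The cost is a text change in both documents and fewer formal significance claims. In particular, a positive viral load or shedding result after a failed primary, or after a failed earlier secondary, would be reported as descriptive. Sample size, data collection and models are unchanged.

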### **11.3 Exploratory analyses**

#### Individual symptom scores based on the Jackson criteria

The individual symptom scores for obstruction, rhinorrhea, cough and sore throat will be analysed similarly as the daily total symptom scores (11.2.5 and 11.2.6).

#### Cytokine response of nasal mucosa

Change in Interleukin-8 assay (IL-8) concentrations both from day -28 until virus challenge and from day 0 onwards will be analysed with repeated measures analysis of covariance models (RM-ANCOVA), by including the change from day -28/ day 0 as a response, treatment, baseline covariate (IL-8 at day -28/ day 0), timepoint and the interaction of timepoint and treatment as explanatory variables. The random effect of subject will be included in the model. Model assumptions will be checked with model diagnostics and normality plots. In case normality

assumptions cannot be confirmed, common transformations (log, square root, inverse) will be used. For the analysis 'not detected' values will be replaced with the detection limit / 2. For the change from day -28 analysis the PP dataset will be used, and for the change from day 0 analysis the infected dataset will be applied.

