The effect of BI-04 on the incidence of respiratory tract illness symptoms in healthy active adults was studied in a randomized, double-blind, placebo-controlled clinical trial [5]. The study was conducted in Australia by the Griffith University. A total of 229 health active adults were randomized to placebo (n = 127) and BI-04 (n = 102) groups. The probiotic was administered with a total daily dose of 2.0×10^9 CFU for 5 months throughout the primary cold and flu season. The participants reported self-assessed symptoms of respiratory illness – scratchy or sore throat, sneezing, runny or stuffy nose – using an online questionnaire. An upper respiratory tract illness (URTI) episode was recorded when two or more symptoms were present for three or more consecutive days. During the study period, subjects in the BI-04 group had 102 (59 single and 43 recurrent) URTI symptom episodes compared to 127 (67 single 60 recurrent) episodes in the placebo group. Recurrent events analysis showed a 27% risk reduction ($p=0.022$) for any URTI episode in the BI-04 group compared to the placebo group. Further analyses indicated that in the BI-04 group there was a significant delay in the onset of URTI symptoms (median time 3.2 months), compared to the placebo group (median time 2.5 months) [6].

A recent study using the experimental rhinovirus challenge model at the University of Virginia (manuscript submitted) assessed the effect of BI-04 on host responses to rhinovirus infection. One-hundred fifty-two seronegative volunteers who had received BI-04 (n=73) or placebo (n=79) for 28 days were challenged with RV39. Administration of study intervention was then continued for five days during collection of specimens for assessment of host response, infection, and symptoms. Fifty-eight probiotic and 57 placebo volunteers met protocol defined criteria for analysis. Analysis of nasal lavage IL-8 concentration as the primary outcome variable revealed significantly higher concentrations of IL-8 on Day 0 prior to virus challenge in the probiotic supplemented volunteers (97 versus 58 pg/mL, respectively, $p=0.25$). In contrast, the IL-8 response (change in IL-8 compared to day 0 over days 1-5) to RV39 challenge was significantly reduced in the probiotic supplemented group (geometric mean ratio for change, probiotic: placebo=0.65, $p=0.03$). The administration of probiotic was associated with a reduction in nasal lavage virus titer and the proportion of subjects with virus

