4.2.2 Study periods

Screening:

- Consent and enrollment (approximately 375 subjects)
- Medical history questionnaire and demographics
- Vital signs and brief physical exam
- Physical activity question
- Review of inclusion/exclusion criteria
- Blood draw for screening neutralization antibody titer (if no antibody screening test has been done in the last 12 weeks)

Day -42 ± 4:

- All subjects begin dietary “run-in” period

Day -28 ± 4: Seronegative subjects only

- Review of inclusion/exclusion criteria
- Pre-probiotic baseline nasal lavage for IL-8 and other cytokines
- Pre-probiotic baseline nasal swab for microbiomics
- Pre-probiotic baseline throat swab for microbiomics
- Blood draw for pre-probiotic transcriptomics studies
- Assessment of concomitant medications
- Randomized to active or placebo probiotic
- Urine pregnancy screen for females

Day -21 ± 2

- All subjects return to study site for new supply of probiotic and compliance review
- AE assessment
- Assessment of concomitant medications

Day -14 ± 2:

- All subjects return to study site for new supply of probiotic and compliance review
- Nasal lavage for multiplex cytokine assays
- AE assessment
- Assessment of concomitant medications

Day -7 ± 2:

- All subjects return to study site for new supply of probiotic and compliance review
- AE assessment
- Assessment of concomitant medications

Day 0:

- Review of inclusion/exclusion criteria
- Assessment of blinding
- AE assessment
- Assessment of concomitant medications
- Urine pregnancy screen for females
- Stool specimen for probiotic compliance and microbiomics
- Nasal swab for microbiomics
- Throat swab for microbiomics
- Throat swab for culture
- Nasal lavage for unanticipated viruses
- Nasal lavage for pre-RV challenge baseline IL-8
- Blood draw for measurement of neutralizing antibody
- Blood draw for pre-RV challenge transcriptomics
- Nasal lavage for multiplex cytokine assays
- Symptom assessment
- Challenge with rhinovirus
- Compliance check/resupply
- Continue probiotic treatment

Day 1-4:

- AE assessment
- Assessment of concomitant medications
- Nasal lavage for quantitative rhinovirus culture
- Nasal lavage for IL-8 measurement
- Nasal lavage for multiplex cytokine assays
- Symptom assessment
- Assessment of the effect of symptoms on physical activity
- Nasal swab for microbiomics (day 3)
- Throat swab for microbiomics (day 3)
- Blood draw for post-RV challenge transcriptomics (Day 2 only)
- Continue probiotic treatment

Day 5:

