5.3 Dosage and Administration

5.3.1 Duration of Treatment

All volunteers will sign consent and be screened for study eligibility before randomization to study product. On day -28 of the study, all volunteers will come to the study site, be randomized to study treatment and instructed when to take the first dose of study product. Volunteers will be instructed to take daily one sachet of the study product mixed into a drink that is not hot and does not contain alcohol. The study product will have a minimal of 2×10^9 cfus of BI-04. On days -21, -14 and -7 subjects will come to the study site for re-supply of the probiotic and for evaluation of compliance. On day 0 the volunteers will be challenged with the study virus. After the virus challenge all volunteers will continue the study treatment on through study day 14.

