#### Multiplex assays: A panel of cytokines and chemokines

A panel of cytokines and chemokines (the following parameters will be analysed: IFN- $\gamma$ , IL-10, G-CSF, MCP-1, IP-10, IL-6, IL-1b) measured will be analysed in exactly the same way as IL-8.

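### Post-challenge IL-8 and cytokines are compared only relative to Day 0, an on-treatment value, so the estimate is not the product's effect on post-challenge levels and can mislead in either direction

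*SAP*

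**What the plan says.** SAP 11.3 (Cytokine response of nasal mucosa) analyses the change in IL-8 "both from day -28 until virus challenge and from day 0 onwards". Both analyses use a repeated-measures ANCOVA, "by including the change from day -28/ day 0 as a response, treatment, baseline covariate (IL-8 at day -28/ day 0), timepoint"; a treatment-by-time term is also fitted. The Day -28 form stops at challenge and uses the PP dataset. The Day 0 form covers everything afterwards, and "for the change from day 0 analysis the infected dataset will be applied". The multiplex panel of seven further cytokines and chemokines "measured will be analysed in exactly the same way as IL-8".

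On timing, Protocol 5.3.1 has volunteers attend on Day -28 to "be randomized to study treatment and instructed when to take the first dose of study product", with daily dosing through Day 14. Protocol 4.2.2 lists, for Day -28, a "Pre-probiotic baseline nasal lavage for IL-8 and other cytokines". That sample does not enter the post-challenge model.

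On the product's effect at Day 0, Protocol 1.1 says that analysis of the earlier BI-04 challenge trial "revealed significantly higher concentrations of IL-8 on Day 0 prior to virus challenge in the probiotic supplemented volunteers" (97 v 58 pg/mL). It then reports a reduced response, measured as change from Day 0 over Days 1-5 (ratio 0.65). It concludes that the product alters the baseline state of the nasal mucosa.

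**The concern.** A baseline covariate gives a clean treatment comparison when treatment cannot have affected it. Day 0 fails that condition here, on the sponsor's own account of the earlier trial. If the product shifts Day 0 IL-8, volunteers with the same Day 0 value in the two arms are no longer comparable. The model then mixes the product's effect before challenge with its effect after challenge.

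Protocol 2.2.3 sets out to validate the product's effect on nasal cytokines both at baseline and during infection. SAP 11.3 plans no inferential comparison of post-challenge levels that avoids Day 0, so the second half of that aim is not estimated. The same model covers eight analytes. SAP 16 also names the IL-8 response for a meta-analysis with the earlier trial.

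The Infected set adds a second condition that depends on events after randomisation.

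**Working it through.** **1. Figures the plan gives.** There is no sample size, SD or slope for the cytokine analyses. The only design figure is 95 completed per arm for the primary endpoint (60% v 40%, 80% power, two-sided 5%). The unpooled formula gives (1.960 + 0.842)² × (0.24 + 0.24) / 0.20² = 7.85 × 12 = 94.2, rounded up to 95. It reproduces. It is used here only to size the simulation: 95 × 0.90 infected = 85.5, so about 85 infected per arm.

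**2. What the coefficient estimates.** Let P be the post-challenge value (mean of Days 1-5), D the Day 0 value and T the arm. The planned model is

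P − D = α + τT + γD + error,

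which is the same as P = α + τT + bD + error, with b = 1 + γ the within-arm slope of P on D. Hence

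τ = (arm difference in P) − b × (arm difference in D).

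Unadjusted change from Day 0 is the case b = 1. The coefficient equals the post-challenge difference only if b = 0 or the arms do not differ at Day 0.

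**3. Illustrative Day 0 difference.** 97/58 = 1.67 and ln(97/58) = 0.514. Two limits apply. The protocol calls this difference significant but prints p = 0.25, and it does not say what kind of average 97 and 58 are.

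**4. Result on the log scale** (b is assumed, because the documents do not give it):

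| b | Post-challenge levels identical (true ratio 1.00): exp(−0.514b) | Same 1.67 ratio persists after challenge (true ratio 1.67): exp(0.514(1 − b)) |
|---|---|---|
| 0.3 | 0.86 | 1.43 |
| 0.5 | 0.77 | 1.29 |
| 0.7 | 0.70 | 1.17 |

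In the first case an absent effect looks like a reduction. In the second a real rise is understated.

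SAP 11.3 transforms only if normality fails, so the default model is on raw concentrations. The identity holds there too. If 97 and 58 are read as means, the difference is 39 pg/mL. With identical post-challenge levels the coefficient is then −0.3 × 39 = −11.7, −0.5 × 39 = −19.5 or −0.7 × 39 = −27.3 pg/mL.

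**5. Simulation check.** Assumptions: 85 infected per arm, log SD 1.0, equal correlation among Day -28, Day 0 and the post-challenge mean (so b equals that correlation), 3,000 runs per case.

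- Day 0 raised, post-challenge levels identical: the planned model is significant in 18%, 46% and 87% of runs at b = 0.3, 0.5 and 0.7. A model adjusted for Day -28 gives a ratio of 1.00 and rejects in 4-5%.
- Equal shift at Day 0 and after challenge: the Day -28 model returns 1.66 to 1.67. The planned model returns the attenuated values in the table.
- No Day 0 shift: both models give about 1.00 and reject in about 5%.
- The rejection rate depends on the SD. At b = 0.5 in the first case it is 72% with SD 0.7 and 23% with SD 1.5, while the ratio stays near 0.77.

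**The case against.** The best defence is replication. The earlier trial defined its response as change from Day 0, so the same metric is needed to compare the two trials. The Day 0 model also answers a legitimate, narrower question: the change given where a volunteer stood just before challenge. Both points stand, and they are reasons to keep the model.

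A second defence is that the plan already contains the antidote. The Day -28-to-challenge model tests the Day 0 shift directly, and Protocol 8.4 promises at least descriptive statistics for every variable. This stands in part, since a careful reader would see a Day 0 shift. But neither item estimates the post-challenge difference with an interval, and the two models use different datasets (PP and Infected), so their results cannot simply be combined.

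A reader might also infer three stronger things that the documents do not support.

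- *That the plan will manufacture a reduced response.* It does so only if Day 0 is raised and post-challenge levels are not. Product continues through Day 14, so a persisting shift is also possible, and the planned model would then show an increase.
- *That the earlier trial's 0.65 was an artefact.* If 0.65 is an unadjusted change, then 0.65 × 1.67 = 1.09, which is no lower level on product. If it was adjusted for Day 0, the implied post-challenge ratio is 0.65 × exp(0.514b) = 0.76, 0.84 or 0.93 at b = 0.3, 0.5 or 0.7. The protocol does not say which it was.
- *That the fallback transformations cannot be computed because change scores go negative.* SAP 11.3 does not say that the change itself is transformed. The half-detection-limit rule that follows fits transforming concentrations. This needs one clarifying sentence.

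**Conclusion.** The concern holds in a bounded form. Every planned post-challenge comparison of IL-8 and the seven panel analytes is conditional on a value measured after about 28 days of product. Its coefficient is not the product's effect on post-challenge levels unless the arms agree at Day 0 or b is zero. Read alone, it cannot distinguish a smaller response to virus from a higher starting point.

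The distortion can go either way, as the table shows. The algebra rests only on the stated model. The sizes rest on a log-scale analysis, the earlier trial's Day 0 ratio and an assumed slope. They illustrate and do not predict. If the product has no Day 0 effect, the problem disappears.

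These are exploratory endpoints, so no primary or hierarchical secondary conclusion depends on them.

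**What to change.** In SAP 11.3, before unblinding:

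- Make the main post-challenge comparison a repeated-measures model of log IL-8, and of each panel analyte, on Days 1-5. Use the log Day -28 value as covariate, with treatment, day and their interaction. Report geometric mean ratios with 95% intervals.
- Run it in all challenged subjects (the SAP's ITT set) and in PP, with the Infected set as supportive.
- Keep the change-from-Day 0 model alongside for comparison with the earlier trial. Label it as conditional on an on-treatment value, and state that it will not be read alone as evidence of a reduced response.
- State that any log transformation is applied to concentrations before a change is taken.

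The cost is SAP wording and one extra model per analyte. The Day -28 and post-challenge lavages are already in the schedule of events, so no new sample is needed. Intervals may be somewhat wider if Day -28 predicts Days 1-5 less well than Day 0 does.
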